8.2.4. Clinical Laboratory Safety Analyses

Clinical chemistry, hematology and other laboratory tests are assessed in this study according to the schedule outlined in the Time and Events table (see Section 10.2.1). The following tests will be summarized in clinical laboratory displays:

Clinical Chemistry	Alanine aminotransferase (ALT)	Aspartate aminotransferase (AST)	Bilirubin (total and direct/indirect)
	Potassium (serum)	Blood urea nitrogen (BUN)	Albumin
	Calcium (albumin corrected)	Phosphate	Creatinine (and eGFR CKD-EPI)

Hematology	Platelet count	RBC indices:	Leukocyte (white blood cell) count with Differential
	Erythrocyte (red blood cell) count	Mean corpuscular volume (MCV)	Neutrophils (absolute and segmented)
	Reticulocyte count	Mean corpuscular hemoglobin (MCH)	Lymphocytes
	Hematocrit	Mean corpuscular hemoglobin concentration (MCHC)	Monocytes
		Erythrocytes (red cell) distribution width (RDW)	Eosinophils
			Basophils

Other Laboratory Tests	Intact parathyroid hormone (iPTH)	High-sensitivity C-reactive protein (hsCRP)	Vitamin B12
	Vitamin B9		

Summaries of central laboratory Hgb values, HemoCue Hgb values, iron parameter values (serum iron, ferritin, hepcidin, TIBC, TSAT), and lipid parameter values (total cholesterol, direct LDL-C, HDL-C) are included in earlier efficacy and safety sections and will not be included with clinical laboratory displays. However, these parameters may be included in PCI summaries.

The clinical chemistry tests performed in this study include ALT, AST and bilirubin. In addition to being summarized with the clinical chemistry values, these laboratory values will be included in some of the Hepatobiliary (liver) displays.

CONFIDENTIAL

201410

In addition to the visits listed for the laboratory assessments in the Time and Events table (see Section 10.2.1), any of these assessments can be performed at an unscheduled/retest visit or at the follow-up visit at the discretion of the investigator. See Section 10.5.3 for handling of unscheduled values. The laboratory's normal range values will be provided by the central laboratory and potential clinical importance thresholds are defined in Section 10.8.1.

All of the tabular summaries described below will include summaries in SI units; conventional units will also be provided for the following laboratory tests: MCHC, albumin corrected calcium, creatinine, eGFR, phosphate, albumin, BUN, total cholesterol, LDL-C, HDL-C, and Vitamin B9. Conversions from SI units to conventional units are included in Section 10.6.4. Hemoglobin summaries will only use conventional mg/dL units. Summaries of reticulocytes will be provided for the total count and percent of total erythrocytes and summaries of neutrophils, lymphocytes, monocytes, eosinophils, and basophils will be provided for total counts and differentials (percent of total leukocytes).

The clinical laboratory safety analyses will be based on the Safety population, unless otherwise specified.

8.2.4.1. Overview of Planned Clinical Laboratory Safety Analyses

Table 12 provides an overview of the planned clinical laboratory safety analyses.

Table 12 Overview of Planned Clinical Laboratory Safety Analyses

Parameter	Absolute				Change from Baseline			
	Summary		Individual		Summary		Individual	
	T	F	F	L	T	F	F	L
Clinical Chemistry								
Chemistry Values by Visit	Y				Y			
Worst Case Chemistry Results by PCI Criteria Post-Baseline Relative to Baseline	Y							
Hematology								
Hematology Values by Visit	Y				Y			
Worst Case Hematology Results by PCI Criteria Post-Baseline Relative to Baseline	Y							
Other Laboratory Tests								
Other Laboratory Values by Visit	Y				Y			
Worst Case Other Laboratory Results by PCI Criteria Post-Baseline Relative to Baseline	Y							
Hepatobiliary (Liver)								
Liver Monitoring/Stopping Event Reporting	Y							
Hepatobiliary Laboratory Abnormalities	Y							
Medical Conditions for Subjects with Liver Stopping Events				Y				
Substance Use for Subjects with Liver Stopping Events				Y				
Scatter Plot of Maximum vs. Baseline for ALT		Y						

CONFIDENTIAL

201410

Parameter	Absolute				Change from Baseline			
	Summary		Individual		Summary		Individual	
	T	F	F	L	T	F	F	L
Scatter Plot of Maximum ALT vs. Maximum Total Bilirubin		Y						
All Laboratory								
All Laboratory Data for Subjects with Any Value of PCI				Y				
All Laboratory Data				Y				
Iron								
Worst Case Iron Results by PCI Criteria Post-Baseline Relative to Baseline				Y				

NOTES :

- T = Table, F = Figure, L = Listing, Y = Yes display generated.
- Summary = Represents TFL related to any summaries (i.e. descriptive statistics) of the observed raw data.
- Individual = Represents FL related to any displays of individual subject observed raw data.

8.2.4.2. Planned Clinical Laboratory Safety Display Details*Clinical Chemistry*

Continuous on-treatment values (see Section 10.4.1) will be summarized using mean, standard deviation, minimum, P25, median, P75, and maximum for each scheduled visit and for baseline and end of treatment (see Section 10.6.4) by treatment group.

Continuous on-treatment change from baseline values will be summarized using mean, standard deviation, minimum, P25, median, P75, and maximum for each scheduled visit and for end of treatment (see Section 10.6.4) by treatment group.

The number and percentage of subjects with on-treatment worst case laboratory results relative to PCI criteria (see Section 10.8.1) which are post-baseline relative to baseline will be summarized by laboratory test, category and treatment group. See Section 10.6.4 for additional information on worst case values and PCI categories.

Hematology

The displays presented for clinical chemistry laboratory values will also be presented for the hematology laboratory tests listed in Section 8.2.4.

Other Laboratory Tests

The displays presented for clinical chemistry laboratory values will also be presented for the other laboratory tests listed in Section 8.2.4..

On-treatment hsCRP values will be log-transformed (see Section 10.5.2) and summarized using geometric mean, coefficient of variation, minimum, P25, median, P75, and maximum for each scheduled visit by treatment group.

Percent change from baseline in log-transformed (see Section 10.5.2) on-treatment hsCRP values will be summarized using geometric mean, 95% confidence interval, minimum, P25, median, P75, and maximum for each scheduled visit by treatment group.

Hepatobiliary (Liver)

Please refer to the protocol for details of liver chemistry stopping criteria.

Liver monitoring/stopping events will be summarized by treatment group.

Hepatobiliary laboratory abnormalities will be summarized by treatment group.

Medical conditions for subjects with liver stopping events and substance use for subjects with liver stopping events will be listed.

A scatter plot of maximum on-treatment ALT values versus baseline ALT values will be produced.

A scatter plot of maximum on-treatment total bilirubin (xULN) versus maximum on-treatment ALT (xULN) values will be produced.

All Laboratory

A listing of all laboratory data for subjects with on-treatment laboratory values outside of PCI criteria will be provided.

A listing of all laboratory data will be provided.

Iron parameters

The number and percentage of subjects with on-treatment or post-treatment worst case laboratory results relative to PCI criteria (see Section 10.8.1) which are post-baseline relative to baseline will be summarized by laboratory test, category and treatment group. See Section 10.6.4 for additional information on worst case values and PCI categories.

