6.2. Randomized Treatment Starting Dose, Dose Steps, and Dose Adjustments

6.2.1. Daprodustat Dosing Information

Daprodustat Starting Dose

[figure not shown]
The starting dose of daprodustat will be assigned based on the HemoCue Hgb concentration at randomization (Day 1) (Table 3).

Table 3 Daprodustat Starting Dose (All Subjects)

HemoCue Hgb (g/dL) at Randomization (Day 1)	Daprodustat starting dose (mg, once daily)
≥8 to <9	4
≥9 to ≤10	2
>10	1

Daprodustat Dose Steps

The available dose steps of daprodustat are outlined below. Dose adjustments will result in the daprodustat dose being increased or decreased by one dose step at a time (see Appendix 3, Section 12.3.2 for details). Those receiving the highest dose of daprodustat who require a dose increase will maintain the same dose, while those receiving the lowest dose of daprodustat that require a dose decrease will have doses withheld.

6.2.2. rhEPO Dosing Information

Darbepoetin alfa Starting Dose

For subjects starting HD or PD, the SC/IV darbepoetin alfa dose will be 0.75-1.0 µg/kg rounded to the nearest available dose. Detailed information is provided in Table 4.

Table 4 Darbepoetin Alfa Starting Dose

Weight	Darbepoetin Alfa Starting Dose
<60 kg	40 µg every 4 weeks
≥ 60 kg to <90 kg	60 µg every 4 weeks
≥90 kg to < 120 kg	40 µg every 2 weeks
≥ 120 kg	60 µg every 2 weeks

Darbepoetin alfa Dose Steps

Dose adjustments will be made programmatically by the Interactive Response Technology (IRT) system.

Dose-steps and frequency of administration of darbepoetin alfa are pre-defined in this study ([Appendix 3](#), Section 12.3.1). The SC or IV darbepoetin alfa dose adjustment increases and decreases are generally within 20% and 33% range, with a few increases of 50% based on available dose strengths.

Additional information about the delivery of the respective rhEPO doses is provided in the SRM. Those receiving the highest dose of rhEPO who require a dose increase will maintain the same dose, while those receiving the lowest dose of rhEPO that require a dose decrease will have doses withheld as per the randomized treatment (daprodustat and darbepoetin alfa) dose adjustment algorithm in [Appendix 3](#).

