7.1. Time and Events Tables and Procedures for Subject Follow-up

Table 6 TIME AND EVENTS TABLE FOR SUBJECTS ON RANDOMIZED TREATMENT

Protocol activity (visits ± 1 week, except Weeks 2 and 4 which are ± 3 days)	Screening Week -2 ¹	Randomization (Day 1)	Weeks 2, 6	Full study visit Weeks 4, 16, 28, 40	Abbreviated study visit Weeks 8, 12, 20, 24, 32, 36, 44, 48	Week 52	Unscheduled	Follow-up Weeks 56-58
Written informed consent ¹⁹	X							
IRT system	X	X	X	X	X		X	X
Entry criteria	X	X						
History: medical, hospitalization, transfusion; demography, height	X							
Weight and estimated dry (target) weight	X	X	X	X	X	X	X	X
SBP/DBP ² , HR ²	X	X ² (triplicate)	X	X	X	X ² (triplicate)	X	X
ECG ³	X	X						
Ultrasound of kidneys and adrenal glands	X ⁴							
Randomized treatment dispensing ¹⁶		X		X	X		X ^{5,6}	
Randomized treatment compliance ¹⁶			X	X	X	X	X ⁷	
Iron therapy, transfusions (record in eCRF, if applicable)		X	X	X	X	X		X
Rescue medication (record in eCRF, if applicable)			X	X	X	X		X
Females only: estradiol & FSH (if required)	X							
Serum pregnancy test ⁸ (FRP only)	X	X		X	X ¹⁷	X	X	X
HemoCue Hgb	X	X	X	X	X	X	X	
Hematology ⁹	X	X		X	Hgb only	X	X	X
Clinical chemistry ⁹	X	X		X		X	X	X
Ferritin, serum iron, UIBC	X ¹	X		X		X		X
Vitamin B12 ¹ , folate	X							
Hepcidin		X		X		X		X

Protocol activity (visits \pm 1 week, except Weeks 2 and 4 which are \pm 3 days)	Screening Week -2 ¹	Randomization (Day 1)	Weeks 2, 6	Full study visit Weeks 4, 16, 28, 40	Abbreviated study visit Weeks 8, 12, 20, 24, 32, 36, 44, 48	Week 52	Unscheduled	Follow-up Weeks 56-58
iPTH		X		X		X		X
Storage biomarkers ¹⁸		X		Wk 28		X		
Kt/V _{urea} for dialysis adequacy ¹⁰				X		X		
Lipids (non-fasting), direct LDL		X				X		
PK Sampling ¹¹				Weeks 4, 8, 12 ¹¹				
Genetics sample ¹²		X						
hsCRP		X		Week 28 only		X		
EQ-5D-5L & VAS ¹³ , SF-36 ¹³		X		Weeks 8,12, 28 only		X		
CKD Anemia Symptoms Questionnaire (CKD-AQ) ^{13,14} , PGI-S ¹³	X	X		Weeks 8,12, 28 only		X		
PGI-C ¹³				Weeks 8,12, 28 only		X		
Healthcare resource utilization (subject reported)	X	X	X	Weeks 4,8,12,16, 20, 24, 28 only		X		X
Hospitalization / kidney transplant (record in eCRF, if applicable)			X	X		X		X
Non-serious AEs, SAEs, AEs of Special Interest, clinical events	X ¹⁵	X	X	X	X	X	X	X
Review concomitant medications	X	X	X	X	X	X	X	X

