12.3. Appendix 3: Randomized Treatment Dose Steps and Dose Adjustment Scheme

12.3.1. Darbepoetin Alfa Dose Steps

Total 4-weekly Dose (μg)	PFS Dose and Frequency (PD/HD)
20 μg	20 μg Q4 weeks
30 μg	30 μg Q4 weeks
40 μg^*	40 μg every 4 weeks
60 μg^*	60 μg every 4 weeks
80 μg^*	40 μg every 2 weeks
120 μg^*	60 μg every 2 weeks
160 μg	80 μg every 2 weeks
200 μg	100 μg every 2 weeks
300 μg	150 μg every 2 weeks
400 μg	100 μg once a week

* Subjects starting on these doses at the Randomization (Day1) who have >1 g/dL Hgb decrease or Hgb < 7.5 g/dL at Week 2 or Week 6 from the last visit will receive a “booster” dose of 20 μg in addition to their previous dose.

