Section 7.1, Table 6, Time and Events Table for Subjects on Randomized Treatment. Updated IRT system timing to indicate it is not notified at Week 52.

Revised Text:

Protocol activity (visits ± 1 week, except Weeks 2 and 4 which are ± 3 days)	Screening Week -2 ¹	Randomization (Day 1)	Weeks 2, 6	Full study visit Weeks 4, 16, 28, 40	Abbreviated study visit Weeks 8, 12, 20, 24, 32, 36, 44, 48	Week 52	Unscheduled	Follow-up Weeks 56-58
IRT system	X	X	X	X	X	*	X	X

Section 7.1, Table 6, Time and Events Table for Subjects on Randomized Treatment. Added EGG to screening visit and updated corresponding footnote to clarify ECG can be done between screening and before randomization to treatment.

Revised Text:

Protocol activity (visits ± 1 week, except Weeks 2 and 4 which are ± 3 days)	Screening Week -2 ¹	Randomization (Day 1)	Weeks 2, 6	Full study visit Weeks 4, 16, 28, 40	Abbreviated study visit Weeks 8, 12, 20, 24, 32, 36, 44, 48	Week 52	Unscheduled	Follow-up Weeks 56-58
ECG ³	X	X						

³All ECGs assessment must be recorded pre-dialysis for dialysis subjects. ECG may be performed as early as at screening Week -2 and prior to randomization (Day1).

Section 7.1, Table 6, Time and Events Table for Subjects on Randomized Treatment. Removed randomized treatment dispensing at Week 52 and added Healthcare resource utilization (subject reported) for completeness.

Revised Text:

Protocol activity (visits ± 1 week, except Weeks 2 and 4 which are ± 3 days)	Screening Week -2 ¹	Randomization (Day 1)	Weeks 2, 6	Full study visit Weeks 4, 16, 28, 40	Abbreviated study visit Weeks 8, 12, 20, 24, 32, 36, 44, 48	Week 52	Unscheduled	Follow-up Weeks 56-58
Randomized treatment dispensing		X		X	X	X	X	
Healthcare resource utilization (subject reported)	X	X	X	Weeks 4,8,12,16, 20, 24, 28 only		X		X

Section 7.1. Table 6, Time and Events Table for Subjects on Randomized Treatment. Replaced “MACE” wording with “Clinical events” in order to more accurately represent all safety data being collected.

Revised Text:

Non-serious AEs, SAEs, AEs of Special Interest, MACE clinical events	X ¹⁵	X	X	X	X	X	X	X
--	-----------------	---	---	---	---	---	---	---

Section 7.1. Table 6, Time and Events Table for Subjects on Randomized Treatment. Modified footnote 1 to clarify that Ferritin, TSAT and/or vitamin B12 must be re-assessed, where appropriate, following iron and/or B12 supplementation prior to randomization to meet entry criteria

Revised Text

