10.4.1.2. Treatment States for CV Endpoint Data

Treatment State	Definition
Pre-Treatment	Date < Treatment Start Date
On-Treatment	Treatment Start Date ≤ Date ≤ Last Non-Zero Dose Date + 28 days
Post-Treatment	Date > Last Non-Zero Dose Date + 28 days
Post-Randomization	Randomization Date ≤ Date

NOTES:

- If the last non-zero dose date is missing and the treatment start date is non-missing and Date ≥ Treatment Start Date, then the assessment will be considered to be On-Treatment
- Treatment state definitions use the imputed CV endpoint date

10.4.1.3. Treatment States for BP, Lipid Parameters, Clinical Chemistry, Hematology, Other Laboratory Tests, Hepatobiliary (Liver) and Vital Signs Data

Treatment State	Definition
Pre-Treatment	Date ≤ Treatment Start Date
On-Treatment	Treatment Start Date < Date ≤ Last Non-Zero Dose Date + 1 day
Post-Treatment	Date > Last Non-Zero Dose Date + 1 day
Post-Randomization	Randomization Date < Date

NOTES:

- If the last non-zero dose date is missing and the treatment start date is non-missing and Date > treatment start date, then the assessment will be considered to be On-Treatment

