
Last Non-Zero Dose Date
 
 • Date of last actual dose of randomized study treatment from IP Discontinuation eCRF form. 
 ○ The dose steps used by the dosing algorithm described in the protocol include a dose hold or a zero dose. If subjects are assigned by the algorithm to a zero dose, they do not receive randomized treatment for that period. Hence, it would be possible for a subject to complete the study, while still following the dosing algorithm, but not actually be taking any actual randomized treatment. The last non-zero dose date, then captures the latest date in the study that a subject physically took a dose of randomized treatment. • The eCRF allows for the possibility of partial or missing dates to be recorded for the last actual dose of randomized study treatment on the IP Discontinuation form (i.e., missing day, or day and month, or day and month and year). In such a case, or in case of subjects who have a non-missing treatment start date, but are missing an IP Discontinuation form, the following conventions will be applied in order to impute a last non-zero dose date: 
 ○ Missing day: 
 ▪ The last day of the month will be used, unless the treatment stop date also occurs in the same month; in this case, the treatment stop date will be used. ○ Missing day and month; 
 ▪ ‘31’ will be used for the day and ‘Dec’ will be used for the month, unless the treatment stop date also occurs in the same year; in this case the treatment stop date will be used. ○ Missing day, month, and year: 
 ▪ Treatment stop date will be used only for subjects who have a non-missing treatment start date.

CONFIDENTIAL

201410

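### Both liver scatter plots and the ALT, AST and bilirubin PCI rows stop one day after the last dose, which drops nearly all post-stop liver tests in both arms and gives darbepoetin a shorter window than daprodustat

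*SAP*

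**What the plan says.** SAP 8.2.4.2 plans two liver scatter plots: maximum on-treatment ALT against baseline ALT, and "A scatter plot of maximum on-treatment total bilirubin (xULN) versus maximum" on-treatment ALT. The clinical chemistry PCI table in the same section also uses on-treatment worst-case results. The thresholds in SAP 10.8.1 are 3 times the upper reference limit for ALT and AST and 2 times for total bilirubin. A targeted listing follows the same rule: "A listing of all laboratory data for subjects with on-treatment laboratory values outside of PCI criteria".

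SAP 10.4.1.3, which covers clinical chemistry and hepatobiliary data, defines on-treatment as "Treatment Start Date < Date ≤ Last Non-Zero Dose Date + 1 day". SAP 10.6.1 says that the last non-zero dose date "captures the latest date in the study that a subject physically took a dose of randomized treatment". For darbepoetin that is the date of the last injection, with no allowance for the dosing interval.

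Protocol 12.6.1 (Appendix 6) stops randomized treatment at a liver stopping event. It then asks for a repeat within 24 hours (bilirubin or INR criteria) or 24 to 72 hours (all other criteria), followed by twice-weekly or weekly chemistries until they settle. Daprodustat is taken daily (Protocol 6.1). Darbepoetin is given every 4 weeks, every 2 weeks or weekly, depending on the dose step (Protocol 12.3.1). In Protocol Table 6 the row "Randomized treatment dispensing" has no entry at Week 52, while the clinical chemistry row does.

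**The concern.** The ALT-bilirubin plot is where a reader looks for ALT of at least 3xULN together with bilirubin of at least 2xULN, the pattern that Protocol 12.6.1 treats as possible severe liver injury. Bilirubin can rise after ALT, and the protocol collects the samples that would show it. A window that closes the day after the last dose leaves those samples out of the plot.

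The same window also depends on the dosing interval. Each subject's maximum is therefore taken over a shorter period in the comparator arm, although these displays are meant to be read across arms.

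**Working it through.** **Rule.** A sample counts if its day is no later than the last dose day + 1. Unscheduled values count toward the worst case (SAP 10.6.4.4), so only the date limit excludes them.

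**1. After a stop, both arms.** Take weekly samples 7, 14, 21 and 28 days after the stop. All are more than 1 day after the last dose, so 4 of 4 are excluded in every regimen. Only a repeat drawn by the day after the last dose is kept. A subject stopped on an ALT criterion with bilirubin below 2xULN, and whose bilirubin crosses 2xULN a week later, is plotted outside the joint-elevation region and is not counted in the bilirubin PCI row.

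**2. Week 52, completers on the nominal schedule.** Week 52 is day 52 × 7 = 364. Nothing is dispensed that day, so the last injection is one interval earlier.

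| Regimen | Last dose (day) | Cut-off (last + 1) | Week 52 sample (day 364) | Scheduled chemistries kept |
|---|---|---|---|---|
| Daprodustat daily | 363 or 364 | 364 or 365 | inside | 5 (Weeks 4, 16, 28, 40, 52) |
| Darbepoetin weekly | 364 − 7 = 357 | 358 | 6 days outside | 4 |
| Darbepoetin 2-weekly | 364 − 14 = 350 | 351 | 13 days outside | 4 |
| Darbepoetin 4-weekly | 364 − 28 = 336 | 337 | 27 days outside | 4 |

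Of the 10 darbepoetin dose steps, 4 are every 4 weeks (20, 30, 40, 60 µg), 5 are every 2 weeks (80, 120, 160, 200, 300 µg per 4 weeks) and 1 is weekly (400 µg per 4 weeks). Everyone under 90 kg starts on a 4-weekly step (Protocol Table 4). An elevation first seen at Week 52 on darbepoetin misses both plots and the PCI rows. It also misses the targeted listing unless another value qualifies.

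**3. Monitoring before a stop.** Protocol 12.6.1 stops treatment when ALT of 3 to <5xULN persists for 4 weeks, or ALT of 5 to <8xULN persists for 2 weeks, with weekly samples meanwhile. Let Day 0 be a dosing day with the first raised ALT. The loss depends on whether an injection due on the stop day is given before the ALT result is known.

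| Samples outside the window | Daprodustat | Weekly | 2-weekly | 4-weekly |
|---|---|---|---|---|
| Day 28 stop (samples Days 7, 14, 21, 28), due injection given | 0/4 | 0/4 | 0/4 | 0/4 |
| Day 28 stop, due injection withheld | 0/4 | 1/4 | 2/4 | 4/4 |
| Day 14 stop (samples Days 7, 14), due injection given | 0/2 | 0/2 | 0/2 | 2/2 |
| Day 14 stop, due injection withheld | 0/2 | 1/2 | 2/2 | 2/2 |

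With the injection withheld, the last doses for the Day 28 stop are Day 27 (daprodustat), 21, 14 and 0. For the Day 14 stop they are Days 13, 7, 0 and 0. With the injection given, the last dose is the stop day itself, except for 4-weekly dosing at Day 14, when none is due. In every cell the Day 0 ALT is kept.

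**4. Other windows in the same SAP.** The iron PCI summary (8.2.4.2) and the vital signs PCI summary (8.2.5.2) take on-treatment or post-treatment worst cases. Cardiovascular endpoints count to last non-zero dose + 28 days (10.4.1.2). The SAP gives no reason for the narrower limit on the liver displays.

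**The case against.** The strongest reply has four parts.

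- **Convention.** On-treatment is applied consistently to chemistry, hematology and other laboratory tests. That is true, but the iron and vital signs PCI summaries show that it is not the SAP's universal rule.
- **Coverage elsewhere.** Joint elevations must be reported as SAEs, the full laboratory listing holds every value, and the liver event and hepatobiliary abnormalities tables carry no on-treatment limit. This stands, and it keeps the point modest. It is not complete cover: those tables state no window at all, and the SAE summaries are treatment-emergent, with a window that also ends at last non-zero dose + 1 day (SAP 10.4.1.4).
- **Pre-stop losses.** A reader might infer that darbepoetin subjects routinely lose 1, 2 or all 4 monitoring samples, and with them their ALT PCI row and targeted listing entry. The documents do not support that. ALT is a central-laboratory test (Protocol 7.4.11), dosing follows the on-site HemoCue value, and subjects may stay on treatment during monitoring. The result may therefore arrive after the injection, and for a Day 28 stop the loss can be nil. In this scenario the retained Day 0 ALT is already at least 3xULN, so the PCI row and listing are unaffected. Only a later, higher peak could be lost.
- **Direction.** A reader might also suspect a window that favours daprodustat. Between arms it does the reverse: lower comparator maxima tend to make daprodustat look relatively worse. Dropping post-stop values can understate peaks in either arm.

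**Conclusion.** The concern holds for these displays. The loss of post-stop chemistries is nearly total in both arms and can misplace an evolving ALT-bilirubin case. The arm difference is one scheduled chemistry per completer, 4 against 5. The loss before a stop on darbepoetin ranges from 0/4 up to 1/4, 2/4 and 4/4 samples for a Day 28 stop (weekly, 2-weekly, 4-weekly). For a Day 14 stop it is 0/2 to 1/2, 0/2 to 2/2, and 2/2. Daprodustat loses none.

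These figures assume the nominal schedule. A syringe given late, on the Week 52 visit day or the day before, would bring that sample inside. Values during an approved restart also stay on-treatment, because the last dose in the study sets the limit. The documents give no liver event rate; it is probably low and could be zero. It would be wrong to conclude that liver data are hidden or that SAE reporting is affected. No confirmatory result depends on this. It is a worthwhile correction because it is cheap and because a plot meant for rare cases should not misplace one.

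**What to change.** In SAP 8.2.4.2, define both scatter plots and the ALT, AST and bilirubin PCI rows on the worst-case post-baseline value, on-treatment or post-treatment, using the wording already applied to iron and vital signs. Mark points whose maximum is post-treatment with a separate symbol. Keep the on-treatment version as a companion display, with a footnote that for darbepoetin it ends at the last injection + 1 day. The targeted listing needs the same wording if it is to match.

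A fixed extension would not do the job. With last dose + 28 days, a Day 28 stop and the due injection withheld, post-stop samples fall on Days 35, 42, 49 and 56. The daprodustat cut-off is 27 + 28 = Day 55, which keeps 3 of 4. The 4-weekly darbepoetin cut-off is 0 + 28 = Day 28, which keeps 0 of 4.

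Cost: SAP wording, one date filter, one plot symbol and one footnote. No new samples are needed, since Table 6 and Appendix 6 already require them. The downside is that post-treatment values may reflect other therapy or illness. They are also sampled unequally: after discontinuation, Protocol Table 7 schedules routine chemistry only at the Early Treatment Discontinuation visit. The symbol and the companion display make both visible.
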